11.4.1 Datasets to be analysed, analysis populations

Analysis population: a single group that had the same treatment (per protocol set).

The included subjects are experienced hearing aid users (minimum 6 months) with the same hearing aid model across the population. As hearing loss does not normally fluctuate, we assume that their hearing capabilities are stable over time and that the performance with a hearing aid can be compared over a longer period without any wash out period. Subjects’ individual auditory capacities (hearing loss degree, noise tolerance, speech recognition) vary, however the sample is considered as a homogenous population regarding their experience with the RMD. It will be ensured that the acceptance to generic amplification via hearing aids is not tested but an actual evaluation of the difference between the RMD and the IMD. A single assignment treatment will be considered representative of clinical intervention, i.e. when an experienced hearing aid user tests the ITE device.

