8.3 Device modifications

The IMD will provide the similar amplification as the RMD; therefore, the subject should not experience any significant negative differences that would make the subjects want to discontinue use of the device. However, if a subject does report such differences, that can be improved with fine tuning, fine tuning can be made to improve the situation enough for the subject to continue with the study. If the subject requests to discontinue they can immediately remove the IMD from their ear and return to using their own BTEs. They will be asked to return the IMD to Bernafon AG, but their data will still be included in the results for the current study. All data will remain encoded because the results are only recorded using the identification code of the subject.

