8.5 Data Collection and Follow-up for withdrawn participants

Any data that is collected will be kept in the data management database. The data will remain encoded because results are only recorded using the identification code of the subject. The analysis and report will include a section based on the data available from all recruited subjects (as the intention to treat ITT) and another section based on the data from the subjects that complete the entire protocol (per protocol PP). Withdrawn subjects will have the same follow-up as those subjects that complete the trial. As all subjects are taken from the Bernafon database, all participants, including those that withdraw, are welcome to return to the clinic for fine-tuning and maintenance as needed.

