9.3.2 Fitting/Second Visit

Fitting Visit, Day 10 +/-7: Otoscopy is performed, and the subjects are fitted with the IMD. Output of the IMD is measured, and the fitting adjusted, if necessary, to better match the electroacoustic output of the previously worn, RMD. They are randomized for the speech testing. Speech tests are made with the OLSA in three conditions: unaided, aided with RMD, and aided with IMD. The subjects return the RMD and held until the third appointment for further speech testing. The subjects return the completed questionnaires from the first visit and are given two more questionnaires (APHAB and product) to complete at home. They are given instructions about the IMD and an IFU with information about the IMD. They are scheduled for the third visit. Any AEs are reported in the CRFs.

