11.3 Statistical criteria of termination of trial

A single statistical analysis is planned once all recruited subjects have completed the trial (per-protocol). No interim analysis is planned and no “stopping rules” are set from a statistical perspective. PI’s and clinician judgement are considered as reliable enough to stop the trial.

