11.5 Handling of missing data and drop-outs

For missing data, the PI will contact the involved subject to evaluate the possibility of getting missing data from a questionnaire by post. If a test subject cannot come to the evaluation visit, after exhausting all the possibilities to reschedule a new one, the devices will be sent back per post. If a subject does not want to adhere to the protocol, he can easily switch back to his own devices and return the IMD.

Dropouts will not be replaced; therefore, extra subjects over the calculated sample amount will be included from the beginning to ensure enough completed cases with all data.

The analysis and report will include two separate sections. The first section is based on data from all recruited subjects (as the intention to treat ITT part) and the second section is based on the data from subjects that complete the entire protocol (per protocol PP). Demographical and audiological data (e.g. hearing loss thresholds, degree, and classification) will be available from all recruited subjects including the withdrawn subjects and will be analysed in the report.

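### The protocol names only the per-protocol set for analysis yet requires unranked ITT and per-protocol sections, and its completer definition drops OLSA pairs already recorded at visit 2

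*Protocol*

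**What the plan says.** Section 11.4.1, which defines the datasets, states: "Analysis population: a single group that had the same treatment (per protocol set". It mentions no other set. Section 11.3 uses the same label: "A single statistical analysis is planned once all recruited subjects have completed the trial (per-protocol".

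Section 8.5 asks for two presentations. The first takes in everyone: "The analysis and report will include a section based on the data available from all recruited subjects (as the intention to treat ITT". The second is restricted to completers, and 8.5 describes it as "another section based on the data from the subjects that complete the entire protocol (per protocol PP". Section 11.5 repeats the pair, beginning with "The first section is based on data from all recruited subjects (as the intention to treat ITT part". Neither section says which presentation decides the hypothesis in 11.1. Section 11.4.2 sets out the primary non-inferiority comparison on the OLSA without naming a set.

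On timing, 9.3.2 has the OLSA done at visit 2 in all three conditions (unaided, RMD, IMD), and 11.4 confirms that visit. It is also the visit at which "the subjects are fitted with the IMD" for the first time. Visit 3 (9.3.3) adds the GÖSA and the preference questionnaire, and the home questionnaires on the IMD are returned then.

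The protocol foresees subjects stopping once they have the IMD. Section 8.3: "If the subject requests to discontinue they can immediately remove the IMD from their ear and return to using their own BTEs". Section 11.5: "If a subject does not want to adhere to the protocol, he can easily switch back to his own devices and return the IMD".

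Two further statements bear on whose data are used. Section 10.1 gives the removal of incomplete data as one purpose of withdrawing subjects whose pain prevents use of the device, whereas 7.4 and 8.3 use withdrawn subjects' data and 8.5 retains them. Section 7.4 provides back-up participants to take the place of withdrawals, whereas 11.5 rules out replacement.

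**The concern.** The report will hold two OLSA results, and the protocol does not say consistently which one answers the formal hypothesis. The section on datasets points to the per-protocol set; the sections on withdrawals and missing data put two sets side by side.

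The per-protocol definition in 8.5 and 11.5 also fits this endpoint badly. It makes inclusion depend on attending visit 3, while the whole primary contrast exists at the end of visit 2. Leaving after visit 2 cannot alter an SRT already recorded, yet it would take that pair out of the set named in 11.4.1. With 15 to 20 subjects planned, one or two pairs matter. At stake is the non-inferiority verdict of 11.1 and 11.4.2, including the possibility that the two sections disagree with no rule to settle it.

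**Working it through.** **Inputs.** SD 1.6 dB and margin 1 dB (11.1); alpha 0.05, used one-sided in the formula, and power 0.80 (11.2); paired t-test (11.4); about 20 subjects (6.1; the synopsis says about 15 to 20). The protocol gives no dropout rate, so k = 1, 2 or 4 of 20 leaving between visits 2 and 3 is assumed.

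**The plan's own figure.** n = (σ(z₀.₉₅ + z₀.₈₀)/δ)² = (1.6 × (1.645 + 0.842)/1)² = 15.83, rounded up to 16. This reproduces 11.2.

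**What the primary contrast needs.** Section 11.1 works with benefit, unaided minus aided. The difference in benefit is (unaided − IMD) − (unaided − RMD) = RMD − IMD. The unaided SRT cancels, so the two aided OLSA SRTs from visit 2 are sufficient.

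**Who is in which set.** Take a subject who completes visit 2 and then returns the IMD and leaves.
- ITT section (8.5, 11.5): the pair is included.
- Per-protocol section (8.5, 11.5): excluded, because the protocol was not completed.
- Set of 11.4.1: excluded if per protocol carries the 8.5 and 11.5 definition, the only one given.

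**Precision.** Power = P(T > t₀.₉₅,ₙ₋₁), where T is noncentral t with n − 1 degrees of freedom and noncentrality √n × 1/1.6, at a true difference of 0 dB. The lower-bound distance is t₀.₉₅,ₙ₋₁ × 1.6/√n.

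| Pairs analysed | Power at 0 dB | Distance from mean to one-sided 95% lower bound |
|---|---|---|
| 20 | 0.853 | 0.619 dB |
| 19 | 0.835 | 0.637 dB |
| 18 | 0.816 | 0.656 dB |
| 16 | 0.770 | 0.701 dB |

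**Disagreement between the sets.** In 400,000 simulated trials of 20 subjects, k leave at random and both sets are tested. The shares with opposite verdicts are:

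| True difference | k = 1 | k = 2 | k = 4 |
|---|---|---|---|
| 0 dB | 4.6% | 7.2% | 12.3% |
| −0.3 dB | 7.4% | 10.9% | 16.7% |

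At 0 dB with k = 4, all tested subjects pass and completers fail in 10.3% of trials; the reverse occurs in 2.0%. The net 8.3 percentage points equal the power loss, 0.853 − 0.770 = 0.083, so the two calculations agree.

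**If leaving were related to the SRT (illustration only).** Completer mean − all-tested mean = (k/20) × (completer mean − leaver mean). Each 1 dB gap between completers and leavers moves the completer mean by 0.05, 0.10 or 0.20 dB for k = 1, 2 or 4. The direction follows the sign of the gap, which the protocol gives no basis to predict.

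**The case against.** **The set is already named.** Section 11.4.1 can be read as choosing per protocol, with the ITT section reported alongside; ranking could be left to the SAP, which is not at hand. This has weight, but two points remain. No sentence in 8.5, 11.4.2 or 11.5 gives the per-protocol result precedence. And if it is the choice, the definition attached to it discards usable primary pairs, which is a weakness of a stated rule and not a gap.

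**11.3 concerns timing.** This stands. The sentence sits under termination criteria and is followed by the exclusion of interim analyses. It mainly fixes one analysis at the end, and its per-protocol label is weak support. A reader might infer that it forbids a second analysis set; the text does not go that far.

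**The 11.4.1 wording differs.** A group with the same treatment might include anyone tested with both devices at visit 2. That is possible, but the label in brackets is defined elsewhere only as completers.

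**The pairs are not lost.** Also correct. Sections 7.4, 8.3 and 8.5 keep these data and the ITT section shows them; only the 10.1 clause on pain points the other way. The precision is lost to the 11.4.1 set, not to the report.

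**Some withdrawals do concern the measurement.** Section 7.4 lists unreliable answers and poor compliance while being tested among reasons for withdrawal. Such an SRT may be invalid, so including every recorded pair without condition would go too far. The fix allows for this.

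**The study is called exploratory.** The synopsis and 6.1 say so, which limits the consequence. Sections 11.1 and 11.2 nevertheless state a formal hypothesis, a margin and a powered sample size, and that verdict needs one set.

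**Conclusion.** The point holds as a should-fix inconsistency with a modest cost. Section 11.4.1 lists only the per-protocol set, 8.5 and 11.5 require two unranked sections, and the only per-protocol definition given excludes subjects whose primary contrast is complete.

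The cost is mainly precision. Under the assumed 1, 2 or 4 random leavers of 20, power drops by about 2, 4 or 8 percentage points, and the verdicts differ in about 5%, 7% or 12% of trials at 0 dB. These sizes rest on the assumed number of leavers and the protocol's SD of 1.6 dB; four of 20 leaving would be a lot for a study of two to three weeks in experienced users.

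Two stronger readings are not supported. A reader might infer that the completer set favours the IMD because dissatisfied users leave. That requires leaving to be related to the OLSA difference, which the protocol nowhere indicates, and a shift could go either way. A reader might also infer that the sample size is wrong; 16 reproduces from the plan's own inputs and is not affected by this point.

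**What to change.** - **11.4.1:** Define the deciding OLSA set as all subjects with both aided OLSA SRTs validly measured at visit 2, regardless of later withdrawal. Exclude a pair only for invalidity of the test itself (the reasons in 7.4 that concern reliability or compliance during testing), documented at the visit and without regard to the result. Make the completer set supportive.
- **8.5, 11.3 and 11.5:** Use the same set names and the same ranking. In 11.3, keep the statement on a single final analysis and drop or correct the per-protocol label.
- **10.1 with 7.4, 8.3 and 8.5:** Reconcile the clause on removing incomplete data with the statements that withdrawn subjects' data are kept and used, so that primary data already collected are analysed. This concerns the data only, not when a subject should stop.
- **7.4 with 11.5 (separate, minor):** State one rule on whether dropouts are replaced.

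The cost is wording in six sections (7.4, 8.5, 10.1, 11.3, 11.4.1 and 11.5). No extra subjects, visits or measurements are needed, and the sample size of 16 stays as it is.

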11.4.2 Primary Analysis

Speech Reception Threshold (SRT) from the OLSA test will be measured under three test conditions: unaided, control (RMD), and test (IMD). Test condition order will be randomized using a Latin square design to control any potential order effect. The difference between control and test condition will be

compared to the non-inferiority margin to test for non-inferiority. The unaided condition will be used as control of the investigational device benefit if non-inferiority could not be shown.

11.4.3 Secondary Analyses

OLSA test:

Switching to superiority test will be considered as recommended by the CPMP (2001):

“If the 95% confidence interval for the treatment effect not only lies entirely above $-M$ but also above zero then there is evidence of superiority in terms of statistical significance at the 5% level ($P < 0.05$). In this case it is acceptable to calculate the P value associated with a test of superiority and to evaluate whether this is sufficiently small to reject convincingly the hypothesis of no difference.”

Hearing loss degree and age will be added in post hoc analysis as covariables.

GÖSA test:

Speech Reception Threshold (SRT) from the GÖSA test will be measured under three conditions: unaided, control (RMD), and test (IMD). Test condition order will be randomized using a Latin square design to control any potential order effect. The benefit of amplification will be evaluated with both tested devices with exploratory analysis. The hypothesis is that there is a significant improvement of SRTs in the aided over the unaided condition with the GÖSA test.

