11.1 Hypothesis

There is little evidence from research literature and experience that with equivalent technology, the IMD might be superior to the RMD for speech reception thresholds. Benefit from a more closed fit might be partially compensated by the larger distance between microphone on the BTE placement. However, we can expect that the performance should be at least as good with the IMD.

SRT benefit expressed in terms of benefit with amplification ($SRT_{unaided} - SRT_{aided}$), will be used as primary outcome in the following hypothesis and sample size calculation. As there is no technical motivation to find a benefit with the IMD, the tested hypothesis should therefore focus on the non-inferiority of the IMD compared to the RMD:

H0: average benefit with the IMD (μ_{IMD}) is not non-inferior to the average benefit with the RMD (μ_{RMD})

$$\mu_{IMD} \leq \mu_{RMD} - \delta$$

H1: average benefit with the IMD (μ_{IMD}) is non-inferior to the average benefit with the RMD (μ_{RMD})

$$\mu_{IMD} > \mu_{RMD} - \delta$$

where δ is the non-inferiority margin.

The non-inferiority margin determination follows the guidelines of Flight & Julious (2016). The non-inferiority margin is defined to be the clinical acceptable difference allowing us to conclude that there is no difference between the treatments. We will base our reflexion on SRT benefit from the validation of the RMD to satisfy the following requirements:

- Assay sensitivity, the RMD should provide a benefit over the unaided condition. This can be verified by the achieved mean benefit of +4 dB SNR (SD = 0.8 dB SNR).
- Constancy assumptions, the IMD will be tested in the same conditions and the eligibility criteria are similar between both studies.
- Minimized bias, to reduce the influence of results variability from natural fluctuation the difference between conditions is used rather than absolute SRT results.

From the reference study, a significant and audible difference could be found between the tested devices. This was also reflected by a difference of 1.3 dB SNR (SD = 1.6 dB SNR) in the SRT scores. The OLSA test manufacturer states that the precision to determine the SRT lies around 1 dB for within subject measures. We can therefore set the non-inferiority margin to 1 dB SNR which correspond to a little bit less than 80 % of an audible effect measured with the test. With a non-inferiority margin of 1 dB, we are still ensuring that the IMD has a positive effect over the unaided condition.

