11.2 Determination of Sample Size

The results with the IMD and the RMD are collected on the same subject. SRTs are continuous and normally distributed data. We can therefore apply the sample size determination for mean difference

on one sample.

The formula to compute the sample size is:

$$n = \left(\frac{\sigma(z_{1-\alpha} + z_{1-\beta})}{\delta} \right)^2$$

With n the sample size, σ the standard deviation from the population, δ the non-inferiority margin, α the type I error, and $1-\beta$ the power of the test.

With the following input: $\sigma = 1.6$ dB SNR, $\delta = 1$ dB SNR, $\alpha = 0.05$, and $1-\beta = 0.8$, we will need a sample size of 16 to satisfy the test hypothesis.

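### The level for the primary non-inferiority conclusion is not fixed consistently (one-sided 5% in 11.2, none in 11.4.2, a 95% interval in 11.4.3), and the stated 80% power at 16 subjects is not reached at either level

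*Protocol*

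**What the plan says.** Four places in the protocol bear on the level of the primary test.

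- **Section 11.1** sets a one-directional hypothesis on SRT benefit (unaided minus aided) and fixes the margin: "We can therefore set the non-inferiority margin to 1 dB SNR".
- **Section 11.2** uses a one-sample formula on the paired differences. It contains z(1-alpha), not z(1-alpha/2), with alpha = 0.05, power 0.8 and an SD of 1.6 dB, and concludes that "we will need a sample size of 16 to satisfy the test hypothesis". Sidedness is not stated in words.
- **Section 11.4.2** says that the difference between the two aided conditions is "compared to the non-inferiority margin to test for non-inferiority". It gives no alpha, sidedness or interval width. Section 11.4 describes the method as a paired t-test shifted by the margin, also without a level.
- **Section 11.4.3** adopts quoted guideline text on switching to superiority, which opens "If the 95% confidence interval for the treatment effect not only lies entirely above" and then names -M and, beyond it, zero. This is the only interval level in the protocol that is set against the margin. M is not defined; it is taken here as the 1 dB margin.

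On numbers, the synopsis plans approximately 15-20 participants and section 6.1 approximately 20. Section 11.5 adds extra subjects for dropouts but does not say how many.

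**The concern.** A one-sided 5% test of non-inferiority is the same as requiring the lower limit of a two-sided 90% interval to lie above -1 dB. Reading the same conclusion from a 95% interval is a one-sided 2.5% test. The sizing implies the first, the switching text assumes the second, and the section that defines the primary analysis does not say which applies.

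The choice sets the chance of declaring a truly inferior device non-inferior at the margin (5% or 2.5%), the observed deficit that is tolerated, and the power. In a trial of this size, each of these moves by a visible amount. Separately, the power claim comes from a normal-approximation formula, whereas the planned test is a paired t-test on a small sample.

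**Working it through.** **Inputs.** From 11.2: SD of the paired difference 1.6 dB, alpha 0.05, power 0.80. From 11.1 and 11.2: margin 1 dB. The true difference is taken as 0, because the formula divides by the margin alone.

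**Step 1: reproduce the stated 16.** n = (SD x (z(1-alpha) + z(power)) / margin)^2.

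- One-sided 5%: (1.6 x (1.645 + 0.842) / 1)^2 = 15.83, rounded up to 16. This matches.
- One-sided 2.5%: (1.6 x (1.960 + 0.842) / 1)^2 = 20.09, rounded up to 21. This does not match.

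The stated 16 therefore belongs to a one-sided 5% test.

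**Step 2: where the two levels part.** At n = 16 the SE is 1.6/4 = 0.40 dB. The t quantiles on 15 degrees of freedom are 1.753 (90% interval) and 2.131 (95% interval). Differences are IMD minus RMD in benefit.

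- Lower 90% limit above -1: the observed difference must exceed -1 + 1.753 x 0.40 = -0.30 dB.
- Lower 95% limit above -1: the observed difference must exceed -1 + 2.131 x 0.40 = -0.15 dB.

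Example: for an observed -0.25 dB the lower limits are -0.95 (90%, above -1) and -1.10 (95%, below -1). At n = 20 (SE 0.358) the corresponding band is about -0.38 to -0.25 dB.

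**Step 3: power of the planned paired t-test.** Power is the probability that a noncentral t with n - 1 degrees of freedom and noncentrality margin x sqrt(n)/SD exceeds the t quantile. At n = 16 the noncentrality is 1 x 4/1.6 = 2.5.

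| Completers | One-sided 5% | One-sided 2.5% |
|---|---|---|
| 16 | 77.0% | 64.7% |
| 17 | 79.4% | 67.7% |
| 18 | 81.6% | 70.5% |
| 20 | 85.3% | 75.5% |
| 23 | 89.6% | 81.7% |

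By the normal approximation that 11.2 uses, n = 16 gives 80.4% at one-sided 5% and 70.5% at one-sided 2.5%. So 80% at 16 is true only of the approximation at one-sided 5%. With the t-test, 80% is first reached at 18 completers (one-sided 5%) or 23 (one-sided 2.5%).

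**Step 4: how often the level would matter.** If the true difference is 0, the chance of falling in the band is the gap in power: 77.0% - 64.7%, about 12%, at n = 16, and 85.3% - 75.5%, about 10%, at n = 20.

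**Step 5: does the superiority rule itself clash?** With n = 16, the 95% interval lies above zero only if the observed difference exceeds 2.131 x 0.40 = 0.85 dB. Any such result is non-inferior at either level. The superiority decision does not conflict with the sizing.

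**The case against.** The strongest reply is that the protocol does imply a level. The hypothesis in 11.1 is one-directional, 11.2 sizes that hypothesis with z(1-alpha) at alpha = 0.05, 11.4 describes a t-test shifted by the margin, and 11.4.2 applies it. Read together, this is a one-sided 5% test. The text in 11.4.3 stands under secondary analyses and its only conclusion is superiority. Since an interval above zero is always above -M, its -M clause never decides anything. One-sided 5% for non-inferiority with a 95% interval for superiority is a coherent pairing, and an interval width is a detail that a statistical analysis plan may supply. The study is also called exploratory.

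Much of this stands. A reader might infer that the protocol makes one and the same result both pass and fail non-inferiority. It does not: for a result in the band of step 2, 11.4.3 as written says only that there is no switch to superiority. A reader might also infer that the sponsor is free to pick the level once the data are known. The documents do not support that either, since alpha is given in advance in 11.2.

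The reply leaves two things unanswered. The adopted text is a single-interval procedure that reads non-inferiority and superiority from the same 95% interval, and no sentence says that a different level is meant for the first step. And the power shortfall exists at the plan's own one-sided 5%, whichever way the level is settled. The exploratory label does not remove the formal hypothesis, margin, alpha and power in 11.1 and 11.2.

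**Conclusion.** The point holds as a mismatch of moderate weight, not as an outright contradiction. One-sided 5% is the more natural reading of 11.1 and 11.2, but 11.4.2 does not state it and 11.4.3 takes over a rule built on one-sided 2.5%. The consequence is limited to observed benefit differences between about -0.30 and -0.15 dB at n = 16, a band that a trial of two truly equal devices would hit about 12% of the time.

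The stated 80% power at 16 is overstated under both readings: slightly at one-sided 5% (77.0%), clearly at one-sided 2.5% (64.7%).

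These figures assume an SD of 1.6 dB for the paired difference, a true difference of 0, normally distributed differences, 16 completers, and M equal to the 1 dB margin. One-sidedness in 11.2 is inferred from the formula and from the exact match to 16.

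**What to change.** State one level in 11.4.2 and restate the power in 11.2 for the paired t-test at that level. Either of two wordings settles it.

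- **(a) Keep one-sided 5%.** Non-inferiority is concluded if the lower limit of the two-sided 90% interval for the IMD-minus-RMD benefit difference lies above -1 dB. The 95% interval in 11.4.3 is reserved for superiority. Power is given as about 77% at 16 completers, with 80% reached at 18, which is within the planned 15-20.
- **(b) Use one two-sided 95% interval for both decisions:** above -1 dB for non-inferiority, above 0 for superiority. Power is given as about 65% at 16 and 76% at 20 completers.

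In either case, say that M in 11.4.3 is the 1 dB margin of 11.1.

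The cost is a few sentences and a less favourable stated power. No extra patients are needed for consistency. If 80% power were to be kept under (b), the plan's formula gives 21 and the t-test 23 completers, both above the planned 15-20; (b) should therefore be chosen with the lower power openly accepted.

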5. STUDY OUTCOMES

5.1 Primary Outcome

The primary outcome variable will be the speech scores measured with two speech tests and in three conditions: unaided, with the control (RMD), and with the new device (IMD). Speech scores should be equal to or better than those achieved with the RMD. A non-inferiority test will measure whether the location of the IMD microphones provide as good as or better speech scores than the location of the RMD microphones with a reference speech test. The second test uses different speech material to measure the microphone location effect and should generalize the results to wider listening conditions. The unaided condition will be used as a control of the IMD benefit if superiority cannot be shown.

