9.3.3 Final/Third Visit

Final Visit, Day 28 +/- 5: The subjects will return the completed questionnaires. They are randomized for the speech testing. Speech tests are made with the GÖSA in three conditions: unaided, aided with RMD, and aided with IMD. They return the IMD and can continue to use their own BTEs as normal. The subjects will complete a preference questionnaire to determine if they preferred the IMD or the RMD. They are notified that the study has ended. They are given their reimbursement and instructed to continue using the clinic at Bernafon for routine device maintenance. Any AEs are reported in the CRFs.

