11.4 Planned Analyses

The analysis and documentation will be done by the statistician using R (version 3.4) a statistical software package. R “stats” package will be used for the confidence interval, non-inferiority, and Wilcoxon tests. Documentation of the analysis will be done with R Studio under R Markdown format.

Main outcome: speech reception threshold (SRT from OLSA and GÖSA)

SRTs from the OLSA test are measured during the second visit. OLSA data from a previous trial (BF001-1611) are used for the hypothesis definition, the non-inferiority margin, and the sample size calculation.

The rationale for the analysis is: paired t-tests usually test that the mean differences are zero. The non-inferiority test compares the difference to a non-zero quantity δ . The assumptions of the paired t-test are:

1. The data are continuous (not discrete).
2. The data, i.e., the differences for the matched-pairs, follow a normal probability distribution.
3. The sample of pairs is a simple random sample from its population. Everyone in the population has an equal probability of being selected in the sample.

SRTs from the GÖSA test are measured during the third visit. The GÖSA speech material is different than the OLSA, because it uses different vocabulary and presentation levels. The GÖSA contains short everyday sentences while the OLSA uses standardized, meaningless sentences. Collecting data from two different speech materials should help to generalize our findings. However, due to different test properties (Kollmeier et al., 2011), a separate analysis must be conducted with each test. As we don’t have reference data for the GÖSA test, we cannot compute a non-inferiority margin.. Therefore, the GÖSA analysis is planned as a secondary analysis and described in section 11.4.3.

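### GÖSA is included to measure the microphone-location effect, but its only stated hypothesis is aided versus unaided and no IMD-RMD contrast is named for it

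*Protocol*

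**What the plan says.** **Purpose.** Section 5.1 describes GÖSA this way: "The second test uses different speech material to measure the microphone location effect and should generalize the results to wider listening conditions". Section 4.2 ties the microphone-location effect to comparing speech scores with the IMD against those with the RMD. Section 9.2.1 and the opening of section 11 define the primary outcome as that comparison and list both OLSA and GÖSA. Section 11.4 repeats the generalising aim: "Collecting data from two different speech materials should help to generalize our findings". Section 11.4.1 describes the study as one in which "the acceptance to generic amplification via hearing aids is not tested but an actual evaluation of the difference between the RMD and the IMD".

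**Analysis.** Section 11.4 explains that without GÖSA reference data "we cannot compute a non-inferiority margin", makes the GÖSA analysis secondary, and refers to 11.4.3 for its description. There the plan is: "The benefit of amplification will be evaluated with both tested devices with exploratory analysis". The one hypothesis follows: "The hypothesis is that there is a significant improvement of SRTs in the aided over the unaided condition with the GÖSA test".

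**Data.** Section 9.3.3 collects everything a device comparison needs: "Speech tests are made with the GÖSA in three conditions: unaided, aided with RMD, and aided with IMD".

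**The concern.** The hypothesis in 11.4.3 answers whether amplification helps. The purpose in 5.1 asks whether moving the microphone into the ear changes speech scores. A device can pass the first test by a wide margin and still be worse than its comparator.

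If both devices beat the unaided condition on GÖSA, that result could be presented as the OLSA finding carrying over to a second speech material, although it says little about the device difference. If only the two benefits are reported, a reader can subtract them to get a point difference. Its precision is not recoverable, because it depends on the within-subject correlation. A device contrast chosen after the data are seen, in an open-label study, would also carry less weight than one named beforehand.

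The confirmatory OLSA test is not at stake.

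**Working it through.** **The plan's own figure.** The only sample size stated is for OLSA (11.2): n = (σ(z₁₋α + z₁₋β)/δ)², with σ = 1.6 dB, δ = 1 dB, α = 0.05 and power 0.80. This gives (1.6 × (1.645 + 0.842)/1)² = 15.83, rounded up to 16, so it reproduces. The protocol gives no GÖSA figure.

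**Inputs for the illustration**
- RMD benefit over unaided: 4 dB, SD 0.8 dB (11.1, OLSA). Carrying this to GÖSA is an assumption; 11.4 itself says the two tests have different properties. The benefit SD is therefore varied over 0.8, 1.6 and 2.4 dB.
- SD of the IMD-RMD difference: 1.6 dB (11.1 and 11.2, OLSA), varied from 1.2 to 2.0 dB.
- n = 16 (11.2) and n = 20 (6.1).
- Assumed IMD deficit: 2 dB, twice the OLSA margin, so the true IMD benefit is 4 − 2 = 2 dB.

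**Step 1: would the stated GÖSA hypothesis detect that deficit?** For a two-sided 5% one-sample t-test on benefit, the power is P(T > t₀.₉₇₅,ₙ₋₁), where T is noncentral t with noncentrality √n × benefit/SD. At n = 16 and SD 1.6 the noncentrality is 4 × 2/1.6 = 5.

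| Benefit SD (dB) | n = 16 | n = 20 |
|---|---|---|
| 0.8 | >0.999 | >0.999 |
| 1.6 | 0.9965 | 0.9996 |
| 2.4 | 0.876 | 0.942 |

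These are the chances that the inferior IMD still shows a significant benefit. The RMD, at 4 dB, does so almost surely in every cell.

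**Step 2: what would a paired contrast show?** The 95% CI half-width is t₀.₉₇₅,ₙ₋₁ × SD/√n. At n = 16 and SD 1.6 this is 2.131 × 1.6/4 = 0.853 dB.

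| SD of difference (dB) | Half-width, n = 16 | Half-width, n = 20 | P(CI excludes 0), 2 dB deficit, n = 16 | Same, 1 dB deficit |
|---|---|---|---|---|
| 1.2 | 0.64 | 0.56 | >0.999 | 0.876 |
| 1.6 | 0.85 | 0.75 | 0.9965 | 0.647 |
| 2.0 | 1.07 | 0.94 | 0.962 | 0.465 |

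**Step 3: both together.** In 20,000 simulated trials (n = 16, 2 dB deficit, SD of difference 1.6), both aided-versus-unaided tests were significant while the paired interval lay wholly below zero in 99% of trials at benefit SD 1.6, and in 87% at benefit SD 2.4.

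**Step 4: are two separate benefits enough?** With SD 1.6 dB for each benefit and correlation r, the SD of their difference is 1.6 × √(2(1 − r)). At n = 16:

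| r | SD of difference (dB) | Half-width (dB) |
|---|---|---|
| 0 | 2.26 | 1.21 |
| 0.5 | 1.60 | 0.85 |
| 0.9 | 0.72 | 0.38 |

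The same two summaries are compatible with a threefold range of precision.

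**The case against.** The strongest reply is that the protocol does compare the devices on GÖSA. Sections 9.2.1 and 11 name the IMD-RMD comparison with both tests. Section 11.1 defines benefit as unaided minus aided SRT and states the device hypothesis in that variable, so evaluating benefit with both devices could be read as producing the quantity to be compared. On this reading, naming a paired interval for an exploratory analysis is detail for a statistical analysis plan, which may exist. All conditions are measured in the same subjects at one visit, so nothing prevents the paired calculation.

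Part of this stands. A point difference can be obtained, the data allow a paired interval, and an analysis plan could add one. But 11.4.3 is where the protocol sends the GÖSA analysis, and it goes further than leaving detail open: it states a hypothesis, and that hypothesis concerns a different contrast. By comparison, 11.4.2 does name the control-test difference for OLSA. Sections 9.2.1 and 11 therefore sharpen the mismatch.

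The missing margin rules out a GÖSA non-inferiority test; it does not rule out an estimate with an interval. The sentence in 11.4.1 mainly explains why experienced users are enrolled, so it is supporting evidence only.

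The magnitude is also open to challenge. Every GÖSA value is borrowed from OLSA, and section 3.1 expects only small differences between devices. For a 1 dB deficit the paired interval would exclude zero only 47% to 88% of the time at n = 16. That limits what GÖSA can show about small differences, but it does not make the aided-versus-unaided hypothesis informative about them.

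**Conclusion.** The concern holds. The purpose given to GÖSA in 5.1 and the hypothesis given in 11.4.3 address different contrasts, and no IMD-RMD estimate is named for the test. That conclusion rests on the text alone.

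Its practical size rests on carrying OLSA values over to GÖSA. Under that assumption, a device deficit of twice the OLSA margin would leave the stated hypothesis met with probability 88% to above 99% at n = 16 (94% to above 99.9% at n = 20), while a paired interval would usually reveal the deficit. This should be fixed, but it is confined to a secondary, exploratory analysis.

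**What to change.** In 11.4.3, add the within-subject IMD-RMD difference in GÖSA SRT with a two-sided 95% confidence interval as a named secondary estimate, beside the aided-versus-unaided contrasts. State that it carries no margin and no non-inferiority claim. If no device comparison is intended with GÖSA, narrow the purpose stated in 5.1 and 11.4 instead, and align 9.2.1 and the opening of section 11 with it.

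The cost of the first option is one sentence. All three GÖSA conditions are already measured at the third visit, so no further visit, test, device or participant is needed, and the OLSA analysis stays as written.
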